7.7.6 Safety Review Committee

The SRC will be chaired by the Sponsor Study Team Physician (or delegate) and include the Investigator (or delegate) from each of the investigational sites. In addition, other physicians such as the Global Safety Physician (or delegate) or a senior physician from the same or another project, as well as the Clinical Pharmacology Scientist, Study Statistician, Patient Safety Scientist, Associate Director Study Management, and others may be invited as

appropriate. Further internal or external experts may be consulted by the SRC as necessary. The Global Safety Physician or delegate should always be present at the SRC if there are safety issues for discussion. The SRC Remit document for this study will define the exact membership and who should be present for decisions to be made.

The SRC will review and assess all available safety data from the cohort, with available PK and pharmacodynamics data to determine the dose for the next cohort of patients. Any dose interruptions and reductions (see Section 5.5 for dose modifications) will be taken into account.

Once a DLT has been observed, SRC may decide to:

1. Expand the cohort to include additional patients
2. De-escalate the dose either to a previous lower dose level (up to a maximum of 6 evaluable patients) or to an intermediate lower dose level
3. Stop the arm enrolment

When there are other patients ongoing at the time of this review, the SRC may decide to defer their decision until these further patients become evaluable.

Any patient started on treatment in error (e.g., he/she failed to comply with all of the selection criteria) who meets the criteria of a DLT evaluable patient will be reviewed on a case-by-case basis by the SRC to determine if the patient's data should be included or excluded in the decision for dose escalation.

The decisions and decision-making of the SRC on the next dose level will be documented and provided to the Investigators before dosing any new patients.

7.7.7 Confirmation of the presumed recommended dose

Once the MTDs for each of the 2 agents in combination with MEDI4736 and/or MEDI4736/tremelimumab have been identified or the maximum doses of each of the 2 agents in combination with MEDI4736 and/or MEDI4736/tremelimumab have been reached, the SRC may decide to enroll an additional cohort of at least 6 evaluable patients per treatment arm to confirm the presumed recommended dose for each of the 2 agents in combination with MEDI4736 to be further explored in the dose-expansion Part B.

Dose-expansion Part B

Once the doses for AZD9150 and AZD5069 in combination with MEDI4736 have been established in Part A of the study as detailed in Section 5.3, the dose-expansion Part B will begin. If the RP2D combination is established earlier in one arm of Part A than the other, the Sponsor may manually assign patients to a pretreated arm (treatment arm B1/B2 as discussed below) of the determined RP2D combination to get safety data (for US sites ONLY). One

such patient was manually randomized to Arm B1; this patient will not be included for any efficacy analysis and could be replaced with an actual randomized patient. The doses for the monotherapy treatments will be determined by the SRC based on the experience with the 2 agents gained in other trials and available at that time.

In the dose-expansion Part B, based on the patient's history of treatment with any anti-PD-(L) 1 antibody, the Investigator will assess whether the patient will be assigned treatment in 1 of the anti-PD-(L)1 pretreated arms or naïve treatment arms. Additionally, Arms B7 and B8 will enroll patients who are PD-(L)-1 treatment naïve and have not received any prior systemic treatment for recurrent metastatic SCCHN. Also additionally, based on the patient's history of taking any drugs, herbal supplements, and/or foods prohibited with concurrent administration of AZD5069 or within 14 days of the first dose of AZD5069 and detailed in Section 5.1.2 as well as the patient's anticipated need or likelihood to consume such products at any time throughout the study, the Investigator will further assess each patient enrolled in the study to determine if the patient may be treated with AZD5069. Details regarding study arms for Part B can be found in Section 4.2.

The dose-expansion Part B will use an adaptive approach to sample size based on Bayesian statistical methodology and so the number of actively enrolling treatment arms may decrease as the study continues. See Section 8.2.2 for details on sample size, conditions for stopping an arm, and the conduct of an interim analysis.

7.7.8 Definition of efficacy evaluable patient

As described in Section 8.2.2, the dose-expansion Part B is based on efficacy evaluable patients. Patients identified as not efficacy evaluable will be replaced.

An efficacy evaluable patient is defined as a patient with unidimensional measurable disease at baseline as per the RECIST v1.1 criteria, meeting all eligibility criteria, and who received at least 1 dose of study treatment. For combination arm patients this population will hence include all patients who have received at least one dose of combination.

7.8 Concomitant and other treatments

Information on any treatment in the 30 days before starting study treatment and all concomitant treatments given during the study, including start and stop dates as well as the reasons for the treatment, will be recorded in the eCRF. If medically feasible, patients taking regular medication, with the exception of medications restricted during the course of the study (see Table 2 above) or herbal supplements, should be maintained on these medications throughout the study period.

Other anticancer agents, investigational agents, and radiotherapy should not be given while the patient receiving study treatment, although radiation for palliation at focal sites is permitted.

Blood and blood product transfusions, including platelet infusions are allowed at any time during the study.

Patients already receiving erythropoietin at the time of screening for the study may continue the erythropoietin providing they have been receiving it for more than 1 month at the time study treatment is started. Prophylactic erythropoietin should not be started during the 7-day lead-in period and Cycle 1 in Part A (i.e., the DLT Evaluation period) but may be started during Cycle 2 or after at the discretion of the Investigator. There are no restrictions on the use of erythropoietin in Part B of the study.

Antiemetic premedication for nausea and granulocyte colony stimulating factors are permitted for use at the discretion of the Investigator. The use of either prophylactic antiemetic premedication for nausea or granulocyte colony stimulating factors is not permitted during the 7-day lead-in period and Cycle 1 in Part A (i.e., the DLT Evaluation period); it may be started during Cycle 2 or after at the discretion of the Investigator. There are no restrictions on the use of antiemetic premedication for nausea and granulocyte colony stimulating factors in Part B of the study.

Patients may receive treatment with megestrol acetate when prescribed for appetite stimulation.

Patients may receive treatment with corticosteroids and/or bisphosphonates for the treatment of bone metastases.

Patients may take low molecular weight dextran. The use of Coumadin (warfarin) is not permitted in patients treated with AZD5069 but allowed for all other patients. It is recommended that patients treated with an anticoagulant should have their anticoagulation monitored carefully and dose adjusted accordingly.

Patients allocated to treatment with MEDI4736 may not receive live attenuated vaccines during the study and for 30 days after the last dose of MEDI4736. Non-clinical studies have demonstrated that MEDI4736 partially suppressed the primary antibody response to a T cell dependent antigen (keyhole limpet haemocyanin). Secondary antibody responses to this antigen were normal. The relevance of this finding with respect to a human immune response is theoretical; a reduction in humoral immunity may result in a reduced response to vaccination and increased risk of infection.

As described in the previous section, patients treated with AZD5069, coadministration of drugs that are known potent or moderate CYP3A4 inhibitors, potent or moderate CYP3A4 inducers, P-gp substrates with narrow therapeutic index, sensitive CYP2B6 substrates, warfarin or any other coumarin derivatives, BCRP-substrates that reduce blood neutrophils, and any herbal medications should be avoided. See Section 3.8.2 for details and Table 2 for a list of prohibited medications for patients administered AZD5069. Any questions regarding concomitant treatments in these patients should be referred to the Medical Monitor [REDACTED] (see Section 6.10 for contact information).

With the exceptions noted above, other medication that is considered necessary for the patient's safety and well-being, may be given at the discretion of the Investigator and will be recorded in the appropriate sections of the eCRF.

Patients should abstain from donating blood and plasma during the study.

Investigators should carefully assess the risk in relation to benefit of using anticoagulation or other medications that might exacerbate bleeding during study participation. Investigators should consider discontinuation of these agents if the clinical scenario permits it unless discontinuation would be clinically contraindicated. For example, if the clinical condition for which anticoagulation/nonsteroidal anti-inflammatory drugs/aspirin is/are being used may be managed with an alternate agent/s that has a lower risk of bleeding, a substitution should be considered.

7.8.1 Other concomitant treatment

Other medication other than that described above, which is considered necessary for the subject's safety and well-being, may be given at the discretion of the Investigator and recorded in the appropriate sections of the CRF.

8 STATISTICAL ANALYSES BY ASTRAZENECA

8.1 Statistical considerations

- Analyses will be performed by AstraZeneca or its representatives.
- Refer to Statistical Analysis Plan (SAP) for further details.
- For open-label studies, and if there is a regulatory requirement to submit SAP to regulatory agencies with the CSP, the SAP should be signed off before enrolment of the first subject. For all other studies, the SAP will be signed off before review of any potential treatment-revealing data is undertaken (this includes blinded delivery reviews and data monitoring committee reviews). For all situations, a full draft of the SAP should be available to ensure sufficient time to prepare for any blinded or unblinded data review.

8.2 Sample size estimate

8.2.1 Dose-escalation Part A

A CRM-based approach will be used to identify the set of AZD9150/MEDI4736 and AZD5069/MEDI4736 dose combinations where the incidence of DLT is no larger than 33%. In each cohort, up to 3 patients will be initially assessed. Dose-escalation to the next higher dose level for the next cohort group of 3 patients will occur if all 3 patients in the initial cohort complete Cycle 1 without DLT. Following the first DLT, the CRM model will be run and the output made available to the SRC to guide further dosing decisions.

The CRM model will use a stopping criterion based on posterior variance (posterior variance <0.03). When this criterion is met, the model will recommend that the trial be stopped. The dose with expected DLT incidence closest and below 0.33 at this point will be “model estimated” MTD. During trial execution, the SRC will determine the MTD. For the purposes of describing the operating characteristics of the model, the stopping criterion based on the posterior variance will be the only criterion considered. Model performance is measured using simulation methods. In each case, the trial is simulated 10,000 times, and trials that select each MTD among the doses explored are counted. A logistic dose-toxicity model of the following form will be used:

$$p = \{1 + \exp(-a - (\exp(\beta) * \text{dose})^{-1})\}^{-1},$$

where p is the probability of occurrence of a DLT; the intercept, a, is assigned a fixed value equal to 3; and the prior distribution of the slope parameter, beta, is assumed to be normal with mean=0 and variance=1.34.

In the case of AZD9150/MEDI4736, 4 dose levels are included. The start dose is the second highest dose level among the 4 dose levels. This is also the true MTD. The prior model assumes that the second dose is also the MTD. Using the posterior variance criterion above, the model selects the correct dose combination in 60.1% of simulated trials. The model selects the dose below the true MTD in 18.1% of simulated trials, and the dose above MTD in 21.8%

of simulated trials. On average, the number of patients treated at each of the 4 dose levels is 5.7, 4.8, 3.0, and 1.3. The average number of DLTs at each of the 4 doses is 0.7, 1.5, 1.7, and 1.0.

In the case of AZD5069/MEDI4736, 6 dose levels are included. The start dose is the third highest dose among the 6 dose levels. This true MTD is the fourth highest dose among the 6 dose levels. The prior model assumes that the fourth dose is the MTD. Using the posterior variance criterion above, the model selects the correct dose combination in 50.9% of simulated trials. The model selects the dose below the true MTD in 22.2% of simulated trials, and the dose above MTD in 26.9% of simulated trials. On average, the number of patients treated at each of the 6 dose levels is 0.2, 1.2, 5.5, 4.5, 0.8, and 2.9. The average number of DLTs at each of the 6 dose levels is 0.0, 0.0, 0.6, 1.4, 0.45, and 2.3.

In Arm A3; 6-12 patients will be enrolled.

Approximately 18 patients will be enrolled in the safety run-in cohorts of AZD9150 or AZD5069 in combination with MEDI4736 and tremelimumab (Arm A4).

Approximately 40 patients (approximately 20 patients with breast cancer and 20 patients with prostate cancer) will be enrolled in Arm A6.

These sample sizes are selected based on the need to gather and confirm safety, MTD/RP2D, PK/pharmacodynamic information in solid relapsed/refractory patient population for further exploration in next trials.

8.2.2 Dose-expansion Part B

The dose-expansion Part B will use an adaptive approach to sample size based on Bayesian statistical methodology (Figure 9).

Anti-PD-(L)1 naïve patients

For the 2 combination arms in the anti-PD-(L)1 naïve patients (B3 and B4), once 12 efficacy outcomes have been observed in the first 12 efficacy evaluable patients in each arm, a predictive power calculation will be used to assess the chance of observing at least 8 of 35 responses (either PR or CR) in each arm. The method of calculating predictive power is based on a parameter free approach to predictive power as it applies to variables that follow a binomial distribution (Jennison and Turnbull 2000). Predictive power (chance to observe at least 8 of 35 responses) will be recalculated following the observation of the efficacy outcome in each efficacy evaluable patient as they were dosed in the trial. If, following the observation of any patient's outcome, predictive power falls below 20%, the arm in which this happens will be stopped. If predictive power remains at or above 20% following the 19th efficacy evaluable patient then an interim analysis will be conducted following the 20th efficacy

evaluable patient. Each of the combination arms will continue to enroll patients up to a maximum of 35 efficacy evaluable patients following the interim analysis if at least 5 of 20 patients have responded with at least a PR.

Predictive power monitoring will not be performed for the 2 monotherapy groups (B5 and B6) in dose-expansion Part B and the 1L RM SCCHN patients in Arm B7. The 2 monotherapy arms will continue recruiting until 12 efficacy evaluable patients have been enrolled in each arm.

Anti-PD-(L)1 pretreated patients

For the 2 combination arms in the anti-PD-(L)1 pretreated patients (B1 and B2), once efficacy outcomes have been observed in the first 10 efficacy evaluable patients in each arm, a predictive power calculation will be used to assess the chance of observing at least 3 of 20 of responses (either partial or complete) in each arm. Predictive power (chance to observe at least 3 of 20 responses) will be recalculated following the observation of the efficacy outcome in each efficacy evaluable patient as they were dosed in the trial. If, following the observation of any patient's outcome, predictive power falls below 20%, the arm in which this happens will be stopped. However, no formal interim analysis will be conducted for the combination arms in the anti-PD-(L)1 pretreated patients.

Recruitment will continue while predictive power is measured. If an arm is to be stopped, no new patients will be recruited but patients who are already on study will continue in accordance with study guidelines outlined in Section 4.

If at least 2 CRs or PRs are observed in the first 20 patients in either of the 2 pretreated expansion arms, an additional 25 to 32 patients may be enrolled to that particular pretreated combination arm.

An efficacy evaluable patient is defined as a patient with unidimensional measurable disease at baseline as per the RECIST 1.1 criteria who received at least 1 dose of study treatment.

Simulation methods (10,000 simulated trials) were used to estimate the operating characteristics of the dose-expansion studies. The expected sample size for a series of true ORR values for the combination therapy arms are presented in Table 14 below. These simulation data show that between 207 and approximately 255 patients are expected to be treated in all 8 randomized arms of the dose-expansion Part B (B1 to B8).

The sample size is based on the operating characteristics of a decision procedure using a beta binomial posterior distribution based on observed data assuming a non-informative prior.

[figure not shown]
Table 14 **Expected sample sizes for a series of true objective response rates for combination therapy in anti-PD-(L)1 naïve and anti-PD-(L)1 pretreated patients**

True objective response rate of combination therapy		Expected sample size ^a
Naïve	Pretreated	
0.25	0.15	121.3
0.25	0.05	121.5
0.25	0.025	121.3
0.15	0.15	114.9
0.15	0.05	115
0.15	0.025	115
0.05	0.15	103.9
0.05	0.05	103.8
0.05	0.025	103.7

^a The results are averaged over the corresponding set of naïve and pretreated values. The expected sample size includes 12 patients in each of the 2 monotherapy arms.

Thus, with the study design and interim assessments as described above, the chance to stop a combination arm in anti-PD-(L)1 naïve patients given an optimistic true ORR value (0.45 for naïve and 0.31 for pretreated patients) is approximately 19.3%. The chance to stop a combination arm in anti-PD-(L)1 pretreated patients is approximately 11.7%. If the true ORR performance of the combination arms is low (i.e., approximately 10% for naïve, 5% for pretreated), the chance that any combination will stop before fully recruiting is >98% for naïve and >94% for pretreated.

Figure 9 Adaptive approach to sample size Part B (B1-B6)

If at least 2 CR or PR are observed in the first 20 patients in either of the 2 pretreated expansion arms (Arm B1 or B2), then an additional 25-32 patients may be enrolled.

In addition, Arms B7 and B8 will enroll patients who have not received prior systemic treatment for RM SCCHN and will receive combination treatment of AZD9150 in combination with MEDI4736. With approximately 48 patients in each arm, the chance that fewer than 12 patients with CR or PR (responding) will be observed, given the true fraction of patients responding is 35%, is 9%. The chance that at least 15 patients responding is observed, given the true fraction of patients responding is 25%, is 20%. In addition, B8 will incorporate predictive power monitoring for futility beginning with the 15th patient. If at any time from the 15th patient through the 48th patient, the chance to observe 13 responses in 48 patients falls below 20%, then the arm will be stopped.

In anti-PD-(L)1 pretreated patients, approximately 10 to 52 patients will be treated in each of the 2 combination therapy arms (B1, B2). In anti-PD-(L)1 naïve patients, approximately 12 to 35 patients will be treated in each of the 2 combination therapy arms (B3 or B4). If in Arm B4, the arm is stopped due to lack of efficacy at the IA (following N=20) a higher dose may be tested under the original sample size requirements (N=35) so the total number of patients in Arm B4 would then be N=55 (N=20 from the original IA and N=35 under the original design for Arm B4). In anti-PD-(L)1 naïve patients, 12 patients will be treated in each of the 2 monotherapy arms (B5, B6). In addition, Arms B7 and B8 each will enroll up to 48 patients who have not received any PD-L1 therapies and have received no prior systemic treatment for RM SCCHN. As a result, the total number of patients in Part B will be between 207 and approximately 255.

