### 3.6.2. Dose-expansion Part B

The sample size is based on the operating characteristics of a decision procedure using a beta binomial posterior distribution based on observed data assuming a noninformative prior.

For a single arm trial with  $N$  planned patients and an interim analysis to occur following  $N_i$  patients ( $N_i < N$ ), where  $n_i$  of the  $N_i$  patients included in the interim response and we need to observe  $n_s$  ( $n_s > n_i$ ) patients in order to declare the trial a success then the predictive probability or the chance to observe at least  $n_s$  patients out of  $N$  patients (at the end of the trial) is:

$$\sum_{k=0}^{N_i} [P(X_1 = k | n_i/N_i) (1 - P(X_2 \leq ((n_s - n_i) - 1) | \mu_k))] ]$$

$X_1 \sim \text{Binomial}(N_i, n_i/N_i)$

$X_1$  ranges from 0 to  $N_i$  and is the possible number of successes observed at an interim with  $N_i$  total observations.

$X_2 \sim \text{Binomial}(N - N_i, \mu_k)$

$X_2$  is the number of successes that remain following the interim necessary to achieve the target at the end of the trial.

The left-hand factor in the expression being summed above is a vector of probabilities that  $k$  responses are observed assuming that the observed response proportion is actually true. The right-hand factor is the probability that at least the balance of the required responses needed is observed in the remaining patients to be observed in the planned sample.

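### Protocol 8.2.2 states a 19.3% chance of stopping a naïve arm at a true ORR of 0.45, but its own rule gives 2.5–5.1%; the Part B total of 207–255 follows from neither source given for it

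*Protocol*

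**What the plan says.** Protocol 8.2.2 sets this rule for B3 and B4. After 12 evaluable outcomes, and again after each later one, calculate the predictive power of reaching at least 8 responses in 35. If "predictive power falls below 20%, the arm in which this happens will be stopped". An arm that passes patient 19 has an interim analysis at 20 and continues to 35 only with at least 5 responders.

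The predictive method is described in three ways. Protocol 8.2.2 calls it "based on a parameter free approach to predictive power as it applies to variables that follow a binomial distribution". The same section, and SAP 3.6.2, refer to a "decision procedure using a beta binomial posterior distribution based on observed data assuming a noninformative prior". SAP 3.6.2 also prints an explicit sum.

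For the design so described, Protocol 8.2.2 gives the chance of stopping a naïve combination arm "given an optimistic true ORR value (0.45 for naïve and 0.31 for pretreated patients) is approximately 19.3" percent. For the pretreated arms: "The chance to stop a combination arm in anti-PD-(L)1 pretreated patients is approximately 11.7" percent.

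On numbers, the text before Table 14 reads: "These simulation data show that between 207 and approximately 255 patients are expected to be treated in all 8 randomized arms". Table 14 ("Expected sample sizes for a series of true objective response rates for combination therapy") runs from 103.7 to 121.5. Its footnote says the two monotherapy arms are included and adds: "The results are averaged over the corresponding set of naïve and pretreated values". The end of 8.2.2 gives the same 207 to about 255 as the result of the listed arm limits.

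**The concern.** The 19.3% is presented as a property of the written rule, and the rule is specified closely enough to check. A true ORR of 0.45 lies far above both the 8/35 target (23%) and the 5/20 hurdle (25%), so a one-in-five chance of stopping looks too high. The total has a different problem: one range is credited to two sources that need not agree.

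The stake is the description of the design. A CSR that repeats these figures would tell readers that a highly active arm had roughly a 1 in 5 chance of being closed, and would give a planned size that cannot be traced.

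**Working it through.** **1. Stopping probability, naïve arm, true ORR 0.45**

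Inputs (Protocol 8.2.2): target at least 8 of 35; looks after patients 12 to 19; stop if predictive power is below 0.20; at patient 20, stop with fewer than 5 responses. Outcomes are taken one at a time in dosing order, and probabilities come from an exact recursion over response counts, so there is no simulation error.

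The SAP 3.6.2 formula, with x responses in n patients, is

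PP = Σₖ P[Bin(n, x/n) = k] × P[Bin(35 − n, μₖ) ≥ 8 − x], with μₖ = k/n, replaced by 0.5/n at k = 0 and (n − 0.5)/n at k = n.

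At patient 12 this gives 0.045 for 1 response and 0.268 for 2, so the arm stops with 0 or 1. The full boundary is ≤1 at patients 12–13, ≤2 at 14–18, ≤3 at 19 and ≤4 at 20.

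- Patient 12: 0.55¹² + 12 × 0.45 × 0.55¹¹ = 0.0083
- First crossing at patient 14: 0.0102
- First crossing at patient 19: 0.0022
- First crossing at patient 20: 0.0079
- Total: 0.0287 (unrounded sum)

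The documents do not settle on one formula, so four were used:

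| Predictive formula | One naïve arm | Either of two, 1 − (1 − p)² | ORR at which one arm stops 19.3% of the time |
|---|---|---|---|
| SAP 3.6.2 sum | 2.9% | 5.7% | 0.329 |
| Beta-binomial, uniform prior | 2.5% | 5.0% | 0.325 |
| Beta-binomial, Jeffreys prior | 2.5% | 5.0% | 0.325 |
| Plug-in binomial | 5.1% | 10.0% | 0.352 |

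The 5/20 interim alone gives P(X ≤ 4 | 20, 0.45) = 1.9%. Monitoring on to patient 34 raises the one-arm range only to 2.6–5.2%. With 10,000 simulated trials the standard error at 19.3% is √(0.193 × 0.807 / 10,000) ≈ 0.4 points, so simulation error does not explain the gap.

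**2. Does the same calculation reproduce the neighbouring figures?**

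- Naïve at 10%, stated above 98%: 98.2–98.7% with monitoring past patient 20.
- Pretreated at 5%, stated above 94%: 94.4–95.6%.
- Pretreated at 31%, stated 11.7%: 6.4% (uniform), 7.4% (Jeffreys), 8.8% (SAP sum), 11.0% (plug-in).

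The first two are met and the third is approached, so the rule does not appear to be misread.

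**3. Part B total**

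*From Table 14* (B1–B6, monotherapy included), adding 2 × 48 = 96 for B7 and B8:

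- 103.7 + 96 = 199.7
- 121.5 + 96 = 217.5

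*From the arm limits* (B1, B2: 10–52 each; B3, B4: 12–35 each; B5, B6: 12 each; B7, B8: up to 48 each):

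- Minimum, B7 and B8 both full: 10 + 10 + 12 + 12 + 24 + 96 = 164
- Minimum, B8 stopped for futility at patient 15: 10 + 10 + 12 + 12 + 24 + 48 + 15 = 131
- Maximum: 52 + 52 + 35 + 35 + 24 + 96 = 294; with B4 at 55, 314

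Neither route gives 207 or 255. The two limits differ by 255 − 207 = 48, the size of one first-line arm. On that size the documents disagree: one sentence in the synopsis study design plans B7 and B8 for about 48 in total, while the arm list in the same synopsis, Protocol 4.2.2 and Protocol 8.2.2 give 48 each.

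**The case against.** The best defence is that 19.3% describes something other than one naïve arm. The sentence quotes both the naïve and the pretreated ORR, so its scope is open to doubt. The chance that any of the four combination arms stops is 16.8% (uniform), 18.5% (Jeffreys), 21.6% (SAP sum) or 28.7% (plug-in), which brackets 19.3%. Starting to monitor at the first patient gives 19.5% by the SAP sum and 18.5% by Jeffreys. A wording or scope slip is therefore as plausible as an arithmetic one. Neither scenario is what the sentence says, though. Dropping the 12-patient run-in contradicts the rule, and dropping the 10-patient run-in as well would move the pretreated figure to 19.0% (SAP sum) or 18.3% (Jeffreys), away from 11.7%.

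A reader might go further and infer that 11.7% and Table 14 are wrong too. The documents do not support that.

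- **11.7%.** Plug-in gives 11.0% for one pretreated arm, and the uniform prior gives 1 − (1 − 0.0643)² = 12.4% for either of the two.
- **Table 14.** Protocol 8.2.2 says recruitment continues during monitoring, so overrun belongs to the design, but its size is not stated. Assume 9 extra patients per stopped arm, capped at 35 (naïve) and 20 (pretreated), with no expansion, and average over the pretreated rates. The SAP sum then gives 123.3, 113.0 and 105.8 at naïve ORR 0.25, 0.15 and 0.05, against about 121, 115 and 104 in the table. The 9 is an assumption, but it shows that an ordinary overrun could account for both the level and the flat rows.

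It is also fair to say that little turns on the total in practice. Protocol 4.2.2 reports 155 enrolled in B1–B6, and 155 + 96 = 251 lies inside the stated range. Neither sentence giving 207–255 cites that count.

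**Conclusion.** Two statements in Protocol 8.2.2 do not stand as written.

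- The 19.3% is about four to eight times what the rule gives: 2.5–5.1% per naïve arm, or 5.0–10.0% for either of the two. This assumes outcomes become known one at a time in dosing order, and it holds under every predictive formula tried.
- The range 207 to about 255 follows neither from Table 14 (about 200–218) nor from the arm limits (about 131, or 164 with B7 and B8 full, to 294 or 314). This is plain addition.

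The 11.7% and Table 14 are unconfirmed, not shown to be wrong, because the predictive formula, overrun and expansion handling are not fixed. Figure 9 is not visible in the text reviewed and might add detail.

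A reader might also infer that arms were wrongly stopped or that the efficacy results are affected. Nothing here shows that. The error lies in the description of the rule, not in the rule. Enrolment is closed, the SAP repeats neither 19.3% nor 207–255, and SAP section 8 plans no inferential comparison between arms. Severity is minor.

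**What to change.** In Protocol 8.2.2 or the CSR design section:

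1. Name one predictive formula and re-run the operating characteristics under the written rule. Replace 19.3% with the result, or state the scenario it describes (for example, any of four arms, or monitoring without a run-in).
2. Restate the Part B total with its actual derivation, and say whether B7 and B8 count as 48 each or 48 together.
3. In the same run, confirm 11.7% and state the overrun and expansion assumptions behind Table 14.

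Separately, reconcile two B1/B2 passages. With 2 responses at patient 19, predictive power for 3 of 20 is 10.5–14.3%, so the futility rule stops the arm, while 2 responses in the first 20 permit 25 to 32 more patients. Continued recruitment means both conditions can occur in one arm, and no order of precedence is stated.

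The cost is a short calculation and a wording correction, with no extra patients or data.
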